3.3.2 Exclusion Criteria

1. Patients with neuroendocrine or small cell features are not eligible.
2. Any evidence of metastatic disease. Pre-operative staging will be undertaken per urologic standard of care.
3. Any prior use of hormonal therapy, including:
 - o GNRH agonists or GNRH antagonists (e.g., leuprorelin, degarelix)
 - o Antiandrogens (e.g., bicalutamide, flutamide, nilutamide)
 - o Novel androgen-directed therapies (e.g., abiraterone, enzalutamide)
 - o Any estrogen containing compounds
 - o 5-alpha reductase inhibitors (e.g., finasteride, dutasteride)
 - o PC-SPES or PC-x products. Other herbal therapies or supplements will be considered by the Principle Investigator on a case by case basis based on their potential for hormonal or anti-cancer therapies.
4. Chemotherapy ≤ 21 days prior to first administration of study treatment and/or monoclonal antibody ≤ 6 weeks prior to first administration of study treatment
5. Prior radiation therapy for prostate cancer
6. Prior exposure to BTK inhibitors
7. Prior investigational therapy for prostate cancer
8. Patients may not receive any other concurrent investigational agents while on study.
9. Use of systemic steroid therapy within 28 days of study screening. Patients on inhaled or topical steroids are eligible.
10. Concurrent systemic immunosuppressive therapy within 21 days of the first dose of study drug.
11. Major surgery requiring the use of general anesthetic within 4 weeks of study enrollment
12. HIV, active hepatitis B (HBV) or active hepatitis C (HCV)
 - o Patients with past HBV infection or resolved HBV infection, defined as the presence of hepatitis B core antibody (HBc Ab) and absence of hepatitis B surface antigen (HBsAg) are eligible. HBV DNA must be obtained in these patients prior to day 1 of ibrutinib therapy, but detection of HBV DNA in these patients will not exclude study participation.
 - o Patients positive for HCV antibody are eligible only if polymerase chain reaction is negative for HCV RNA.
13. Inability to swallow capsules or presence of malabsorption syndromes, disease significantly affecting gastrointestinal function, history of resection of the stomach or small bowel, symptomatic inflammatory bowel disease or ulcerative colitis, or partial or complete small obstruction.
14. Currently active, clinically significant cardiovascular disease, such as uncontrolled arrhythmia or Class 3 or 4 congestive heart failure as defined by the New York Heart Association Function Classification; or a history of myocardial infarction, unstable angina, or acute coronary syndrome within 6 months prior to screening.
15. Uncontrolled concurrent illness, or any underlying medical condition, which in

the Principal Investigator's opinion will make the administration of ibrutinib hazardous or obscure the interpretation of adverse events.

16. Recent infection requiring systemic treatment that was completed within 14 days prior to the first dose of study drug
17. Concurrent active malignancy other than non-melanoma skin cancers. Patients are considered to be free of active malignancy if they have completed curative therapy and have a <30% risk of relapse.
18. History of congenital bleeding diathesis.
19. Known bleeding disorders (e.g. von Willebrand's disease or hemophilia).
20. Concomitant use of anticoagulants including warfarin, other Vitamin K antagonists, and enoxaparin.
21. Subjects who received a strong or moderate cytochrome P450 (CYP) 3A4 inhibitor within 7 days prior to the first dose of ibrutinib or patients who require treatment with a strong or moderate cytochrome P450 (CYP) 3A inhibitor.
22. Vaccination with live, attenuated vaccines within 4 weeks of first dose of study drug.
23. Patients on anti-platelet agents including clopidogrel and glycoprotein IIb/IIIa inhibitors. Aspirin is allowed, but should be held before surgery according to standard practices.
24. Currently active, clinically significant hepatic impairment Child-Pugh class B or C according to the Child-Pugh classification
25. Any life-threatening illness, medical condition, or organ system dysfunction that, in the investigator's opinion, could compromise the subject's safety or put the study outcomes at undue risk.
26. Unresolved toxicities from prior anti-cancer therapy, defined as having not resolved to CTCAE v 4.03 grade 0 or 1 or to the levels dictated in the eligibility criteria with the exception of alopecia.

3.3.3 Inclusion of Minorities

Members of all races and ethnic groups are eligible for this trial.

3.4 Duration of Therapy

In the absence of treatment delays due to adverse events, treatment may continue until:

- Administration of all planned doses is completed
- Inter-current illness that prevents further administration of treatment
- Unacceptable adverse event(s)
- Patient decides to withdraw from the study
- Significant patient non-compliance with protocol
- General or specific changes in the patient's condition render the patient unacceptable for further treatment in the judgment of the investigator

3.5 Duration of Follow Up

Patients will be followed for 4 weeks after radical prostatectomy. Patients removed from study for unacceptable treatment related adverse event(s) will be followed until resolution or stabilization of all treatment related adverse events to grade 2 or lower.

4 REGISTRATION PROCEDURES

Patients must not start any protocol intervention prior to registration through the Siteman Cancer Center.

The following steps must be taken before registering patients to this study:

1. Confirmation of patient eligibility
2. Registration of patient in the Siteman Cancer Center database
3. Assignment of unique patient number (UPN)

4.1 Confirmation of Patient Eligibility

Confirm patient eligibility by collecting the information listed below:

1. Registering MD's name, and your institution name
2. Patient's race, sex, and DOB
3. Three letters (or two letters and a dash) for the patient's initials
4. Copy of signed consent form
5. Completed eligibility checklist, signed and dated by a member of the study team
6. Copy of appropriate source documentation confirming patient eligibility

4.2 Patient Registration in the Siteman Cancer Center OnCore Database

All patients must be registered through the Siteman Cancer Center OnCore database.

4.3 Assignment of UPN

Each patient will be identified with a unique patient number (UPN) for this study. All data will be recorded with this identification number on the appropriate CRFs.

4.4 UCSF Patients

The 3 patients enrolled at UCSF will be registered to the Siteman Cancer Center OnCore database, and UCSF will provide study data to the Washington University study team.

5 STUDY DRUGS

5.1 Ibrutinib

Ibrutinib capsules are provided as a hard gelatin capsule containing 140 mg of ibrutinib. All formulation excipients are compendial and are commonly used in oral formulations. Refer to the ibrutinib Investigator's Brochure for a list of excipients.

The ibrutinib capsules will be packaged in opaque high-density polyethylene plastic bottles with labels bearing the appropriate label text as required by governing regulatory agencies. All study drug will be dispensed in child-resistant packaging.

Refer to the Pharmacy Manual/site investigational product manual for additional guidance on study drug storage, preparation and handling.

Study drug labels will contain information to meet the applicable regulatory requirements.

5.1.1 Classification

Cytotoxic drug: molecular targeted cytotoxic drug

5.1.2 Mechanism of Action

Ibrutinib is a potent (IC_{50} 0.39nM) orally bioavailable small-molecule inhibitor of Bruton's tyrosine kinase (BTK). With only a few exceptions, a 10-fold or greater selectivity was demonstrated for BTK relative to off-target kinases. Upon oral administration, Ibrutinib binds to cysteine 481 of BTK and irreversibly inhibits BTK activity, thereby preventing both B-cell activation and B-cell mediated signaling. BTK is a member of the src-related BTK/Tec family of cytoplasmic tyrosine kinases that is required for B cell receptor signaling, plays a key role in B cell maturation, and is overexpressed in a number of B-cell malignancies. The expression of BTK in other tumors has also been associated with increased proliferation, including prostate cancer and breast cancer (Guo W et al, 2014; Eifert C et al, 2013).

5.1.3 Contraindications

Ibrutinib is contraindicated in subjects with clinically significant hypersensitivity, including anaphylactic and anaphylactoid reactions to the compound itself or to the excipients in its formulation.

5.1.4 Availability

Ibrutinib will be supplied by Pharmacyclics Inc.

5.1.5 Storage and handling

Ibrutinib capsules should be stored according to the storage conditions indicated on the label. The recommended storage condition for ibrutinib capsules is 15°C to 25°C (59°F to 77°F) with excursions permitted to 30°C (86°F).

6 TREATMENT PLAN

6.1 Dosage and Administration

Ibrutinib is administered orally once daily on an outpatient basis at a dose of 840 mg. The capsules are to be taken around the same time each day with 8 ounces (approximately 240 mL) of water, with or without food. The capsules should be swallowed intact and subjects should not attempt to open capsules or dissolve them in water. The use of strong CYP3A inhibitors/inducers, and grapefruit and Seville oranges should be avoided for the duration of the study. Examples of inhibitors, inducers, and substrates can be found at <http://medicine.iupui.edu/clinpharm/ddis/main-table/>

If a dose is not taken at the scheduled time, it can be taken as soon as possible on the same day with a return to the normal schedule the following day. The subject should not take extra capsules to make up the missed dose.

The first dose will be delivered in the clinic on Day 1, after which subsequent dosing is typically on an outpatient basis. Ibrutinib will be dispensed to subjects in bottles at each visit. Study drug may not be shipped to the subject without approval from PCYC and may not be dispensed to anyone other than the subject. Unused ibrutinib dispensed during previous visits must be returned to the site and drug accountability records updated at each visit. Returned capsules must not be re-dispensed to anyone.

6.1.1 Overdose

There is no specific experience in the management of ibrutinib overdose in patients. No maximum tolerated dose (MTD) was reached in the Phase 1 study in which subjects received up to 12.5 mg/kg/day (1,400 mg/day). Healthy subjects were exposed up to single dose of 1680 mg. One healthy subject experienced reversible Grade 4 hepatic enzyme increases (AST and ALT) after a dose of 1680 mg. Subjects who ingest more than the recommended dosage should be closely monitored and given appropriate supportive treatment.

Refer to [Section 10](#) for further information regarding special reporting situations as a result of overdose.

6.1.2 Regimen Description

Study Drug	Premedication; precautions	Route	Schedule
Ibrutinib	No premedication required	Oral	Days 1-28

Ibrutinib is supplied in 140mg capsules. Patients in the safety lead-in will be treated at a dose of 840 mg PO daily x 4 weeks. If fewer than 2 DLTs are observed, patients will continue to be treated at that dose level. If ≥ 2 DLTs are observed, dose de-escalation is required. The first reduction will be to Level -1 (840 mg/d x 2 weeks) and the second reduction (if ≥ 2 DLTs are observed at Level -1) will be to Level -2 (560 mg/d x 2 weeks).

6.1.3 Other Modalities or Procedures

Blood samples for PSA and for immune assays will be collected at baseline, before RP, and after RP. Radical prostatectomy will be performed at Washington University, at least 7 days but not more than 12 days following the last scheduled dose of ibrutinib (Day 36 to 41; See Table 6.1). Information including WBC count prior to surgery, amount of blood loss during surgery and/or any post-operative complication(s) will be included in the safety analysis. As there is a potential for loss of immune cell infiltration within the prostate tissue after >12 days of not receiving ibrutinib, any patient who undergoes RP after 12 days from the last dose of ibrutinib will be included in the final analysis; however, an additional patient will be accrued as replacement. This will keep the treatment uniform in order to

evaluate for immune response. The maximum number of allowed replacement patients is 4.

Standard institutional practices for the care and treatment of surgical patients will be followed before, during, and after each patient's RP. Patients will be informed in the written consent that radical prostatectomy may be delayed due to adverse events resulting from study treatment, at the discretion of the investigator and performing surgeon.

6.1.4 Dose Limiting Toxicities

Each patient in the safety lead-in will be assessed periodically for the development of any toxicity as outlined in Section 7 Study Procedures and Observations. Toxicity will be assessed according to the NCI CTCAE v4.0. Dose adjustments will be made according to the system showing the greatest degree of toxicity.

Dose de-escalation in this study will be based on the occurrence of dose-limiting toxicities (DLTs) that occur during the duration of ibrutinib therapy and the period after the last dose of ibrutinib until the day of surgery. DLTs will be defined as any of the following that are attributable to ibrutinib.

- Any grade 4 toxicity, including hematologic toxicities with the exception of lymphocytosis. Lymphocytosis, in the absence of clinical symptoms, is excluded from DLT, as this may be considered an on-target pharmacodynamics effect of BTK inhibition.
- Any grade 3 toxicity.
- Any recurrence of the same grade 3 toxicity.
- Any delay of RP due to study-drug related toxicity.
- Any complications of RP (e.g., bleeding, delayed wound healing) deemed to be related to study drug.

The dose of study drug should be modified according to the dose modification guidelines, including any of the following toxicities:

- Grade 4 ANC (<500/mm³) for more than 7 days.
- Grade 3 thrombocytopenia (<50,000/mm³) in the presence of clinically significant bleeding events.
- Grade 4 thrombocytopenia (<25,000/mm³).
- Grade 3 or 4 nausea, vomiting, or diarrhea if persistent, despite optimal anti-emetic and/or anti-diarrheal therapy.

Patients who experience a DLT may be removed from protocol therapy and undergo RP at the discretion of the operating surgeon.

6.2 Dose Modifications for an Individual Patient Regardless of Dose Cohort

If a patient experiences any CTCAE v4.0 grade 4 toxicity attributed to treatment, ibrutinib must be discontinued. If a patient experiences any CTCAE v4.0 grade 3 toxicity attributed to treatment, ibrutinib must be held until resolution of the toxicity to grade 1 or the patient's baseline, at which time the patient may resume ibrutinib at 50% of the starting dose. If the patient experiences recurrence of the same grade 3 toxicity while on 50% reduced dose,

ibrutinib must be discontinued. If a grade 3 toxicity does not resolve to grade 1 or the patient's baseline within 2 weeks of holding therapy, ibrutinib must be discontinued.

Ibrutinib Dose Modifications According to Toxicity

Event	Management
Any grade 4 toxicity attributed to treatment	Discontinue ibrutinib
Any grade 3 toxicity attributed to treatment	Hold ibrutinib until \leq grade 1, then resume ibrutinib at 50% starting dose
Recurrence of the same grade 3 toxicity while on half dose	Discontinue ibrutinib
Grade 3 toxicity not resolving to \leq grade 1 within 2 weeks	Discontinue ibrutinib

Clinical judgment of the treating physician should guide the management plan of each patient based on individual benefit/risk assessments.

6.2.1 Dose Modification for Hepatic Impaired Subjects

Subjects who develop acute hepatic toxicity with liver enzymes Grade 3 or higher while on study should be managed per standard dose modification guidelines. Ibrutinib is metabolized in the liver and therefore subjects with clinically significant chronic hepatic impairment at the time of Screening (Child- Pugh class C) are excluded from study participation. Concomitant use of strong CYP inhibitors is not permitted in subjects with chronic hepatic impairment. Refer to Appendix D for Child-Pugh classification. Please refer to the table below for dose modifications due to hepatic impairment.

Dose Modification Guidance for Hepatic Impaired Subjects

	Child Pugh class A (Mild hepatic impairment) *		Child Pugh Class B (Moderate hepatic impairment) **	Child Pugh class C (Severe hepatic impairment)
	Ongoing at time of enrollment		Develops during study	Develops during study
Ibrutinib Dose (daily)	280 mg	280mg	140 mg	Hold until improves to moderate [Class B] or better)

* If further reduction is needed due to non-hepatic toxicity, dose may be reduced to 140 mg. In the event that additional reduction is needed, ibrutinib should be held for non-hepatic toxicity until resolution.

** If further reduction is needed due to non-hepatic toxicity, ibrutinib should be held until resolution.

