1.2.1 Nonclinical studies: Ibrutinib

1.2.1.1 Pharmacokinetics and Metabolism

Following oral administration of ibrutinib at doses ranging from 420 to 840 mg/day, exposure to ibrutinib increased proportionally with substantial intersubject variability. The mean terminal plasma elimination half-life ($t_{1/2}$) of ibrutinib ranged from 4 to 6 hours, with a median time to maximum plasma concentration (T_{max}) of 1 to 2 hours. Despite the doubling in mean systemic exposure when dosed with food, the favorable safety profile of ibrutinib allows dosing with or without food. Ibrutinib is extensively metabolized primarily by cytochrome P450 (CYP) 3A4-mediated metabolic pathways. The on-target effects of metabolite PCI-45227 are not considered clinically relevant. Steady-state exposure of ibrutinib and PCI-45227 was less than 2-fold of first dose exposure implying non-clinically relevant accumulation. About 8% of ibrutinib is excreted in the urine. Ibrutinib exposure is not altered in patients with creatinine clearance (CrCl) > 30 mL/min. Patients with severe renal impairment or patients on dialysis have not been studied. Following single dose administration, the AUC of ibrutinib increased 2.7-, 8.2- and 9.8-fold in subjects with mild (Child-Pugh class A), moderate (Child-Pugh class B), and severe (Child-Pugh class C) hepatic impairment compared to subjects with normal liver function. A higher proportion of Grade 3 or higher adverse reactions were reported in patients with B-cell malignancies (CLL, MCL and WM) with mild hepatic impairment based on NCI organ dysfunction working group (NCI-ODWG) criteria for hepatic dysfunction compared to patients with normal hepatic function.

For the most up to date and comprehensive pharmacokinetics (PK) and product metabolism information regarding ibrutinib, please refer to the current [IB](#).

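### The hepatic rules disagree on which Child-Pugh classes are excluded, and give class A at enrolment 280 mg daily where the regimen sections state 840 mg with no exception

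*Combined protocol and SAP*

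**What the plan says.** **Who is excluded.** Section 3.3 requires every inclusion and exclusion criterion to be met. Item 24 of Section 3.3.2 excludes men with "Currently active, clinically significant hepatic impairment Child-Pugh class B or C according to the Child-Pugh classification". Section 6.2.1 states that those with significant chronic hepatic impairment "at the time of Screening (Child- Pugh class C) are excluded from study participation". Class B is missing from that second sentence. Class A is not excluded in either place.

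**Starting dose.** Section 6.1 reads "Ibrutinib is administered orally once daily on an outpatient basis at a dose of 840 mg". Section 6.1.2 adds "Patients in the safety lead-in will be treated at a dose of 840 mg PO daily x 4 weeks". Section 3.1 also enrols patients at 840 mg daily for 4 weeks. The table in Section 6.2.1 has a class A entry headed "Ongoing at time of enrollment" with a daily dose of 280 mg. Its footnote treats 280 mg as the level from which any further step is taken: "If further reduction is needed due to non-hepatic toxicity, dose may be reduced to 140 mg".

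**Exposure.** Section 1.2.1.1 reports a single-dose AUC 2.7 times higher in class A than with normal liver function. It also reports more grade 3 or higher reactions in B-cell malignancy patients with mild hepatic impairment, classified there by the NCI organ dysfunction criteria.

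**Classification.** Appendix 4 assigns 5 to 6 points to class A. Section 6.2.1 sends the reader to an Appendix D, but the appendices are numbered 1 to 6 and the Child-Pugh score is in Appendix 4.

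**The concern.** Two site staff reading different sections could reach different starting doses for the same eligible man with class A impairment. That is a safety matter first, because the protocol itself reports altered exposure in this group.

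It is also a statistical matter. The lead-in judges one regimen, 840 mg for 4 weeks, in six patients. Section 12.5 requires de-escalation at two or more patients with DLTs. Section 12.3 then carries those six into a total of 24 at the MTD. A man started at 280 mg has not received the regimen under test, and no section says whether he counts in either number.

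The disagreement over class B matters less in practice. It still leaves the protocol with two different statements of one exclusion, and one of them is contradicted by the table beneath it.

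**Working it through.** No power or sample-size figure is involved, so there is none to reproduce. The check is a comparison of text plus simple ratios.

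**Step 1. Exclusion by class**

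| Class at screening | 3.3.2 item 24 | 6.2.1 sentence | 6.2.1 table |
|---|---|---|---|
| A | not excluded | not excluded | entry for impairment present at enrolment |
| B | excluded | not named | only as arising on study |
| C | excluded | excluded | only as arising on study |

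The sentence and item 24 differ for class B alone. The table has no at-enrolment entry for B, so it agrees with item 24.

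**Step 2. Starting dose for an eligible class A man**

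- Sections 3.1, 6.1 and 6.1.2: 840 mg daily.
- Section 6.2.1 table: 280 mg daily.
- Ratio: 840/280 = 3, or 280/840 = 0.333.
- The lowest planned dose level (Level -2) is 560 mg daily, reached only after DLTs. 280/560 = 0.5, so the tabled dose is half the lowest level of the design.

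A second class A cell in the table has lost its sub-heading in the text available here. Both cells read 280 mg, so the comparison does not depend on it.

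**Step 3. Knock-on in the modification rules**

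Section 6.2 resumes at 50% of the starting dose after a grade 3 toxicity. That is 0.5 × 840 = 420 mg under one reading and 0.5 × 280 = 140 mg under the other. The ambiguity in starting dose passes straight into this rule.

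**Step 4. Weight of such a man in the design**

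The documents do not give the number affected. For k such men among the six in the lead-in, or among the 24:

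- k = 1: 1/6 = 16.7% of the lead-in; 1/24 = 4.2% of the total.
- k = 2: 2/6 = 33.3%; 2/24 = 8.3%.

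With de-escalation set at two patients with DLTs, one patient supplies half the trigger, or one patient on a third of the dose supplies a sixth of the reassurance.

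**Step 5. Who is class A**

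Appendix 4 has five measures scored 1 to 3, so the minimum is 5 × 1 = 5 points, which is labelled class A. The score alone therefore does not separate normal liver function from class A. The screening list in Section 8.1.1.2 does not call for a Child-Pugh score.

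**Step 6. How far the laboratory criteria help**

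Section 3.3.1 requires normal PT/INR and PTT, bilirubin below 1.5 times ULN, and AST and ALT below 2.5 times ULN. AST and ALT are not part of the score. Albumin, ascites and encephalopathy are part of it but are not inclusion limits. A man with albumin of 2.8 to 3.5 g/dL and the other four measures at 1 point scores 2 + 4 = 6, class A. Such men can enrol, though probably few will.

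**The case against.** The strongest reply is that 6.2.1 is a specific rule qualifying a general one. It sits under a heading on dose modification for individual patients. The protocol does the same in Section 8.6, which sets 140 mg with certain CYP3A inhibitors and has no matching exception in 6.1. On that reading the defect is a missing cross-reference. This has force, but an entry for impairment present at enrolment fixes a starting dose rather than modifying one, and 3.1, 6.1 and 6.1.2 allow for no other starting dose. Even if the exception is intended, the plan still does not say how the man counts.

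Several stronger inferences are tempting and do not stand:

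- *All patients must receive 840 mg.* No sentence says so. The regimen is stated generally, without an exception.
- *Class B men could enter, so the 8.2-fold AUC reported for class B bears on the starting dose.* Section 3.3 with item 24 keeps them out. The 6.2.1 sentence is incomplete; it does not admit them.
- *Appendix 4 puts every normal man on 280 mg.* Section 6.2.1 and its table speak of hepatic impairment, and Section 1.2.1.1 contrasts class A with normal function. The documents treat impairment as a precondition. A definition is missing, but this is not a further contradiction.
- *The 24-patient basis is destroyed.* That would require such men to enrol in number, which nothing shows. The plan also accepts reduced dosing after toxicity, and Section 12.6.1 analyses everyone who received a dose.

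**Conclusion.** The inconsistency is real and should be corrected. It has three parts:

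- The 6.2.1 sentence names class C where item 24 names B or C, and the 6.2.1 table supports item 24.
- An eligible man with class A impairment at enrolment has two unreconciled starting doses, threefold apart.
- No rule says how a man started below 840 mg counts in the DLT gate or among the 24.

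The size in patients is unknown. The view that it is small is an assumption, resting on the laboratory criteria and on fitness for prostatectomy. The effect on the design is conditional on at least one such man enrolling. It would be felt most in the lead-in, where one man is a sixth of the cohort. The conclusion does not depend on whether 6.2.1 was meant as an exception, because the protocol does not say so and the counting rule is absent either way.

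**What to change.** The sponsor should:

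- reconcile item 24 of Section 3.3.2 with the sentence and table in 6.2.1, so that one set of classes is excluded throughout;
- reconcile the 6.2.1 table with Sections 3.1, 6.1 and 6.1.2, so that one starting-dose rule applies to each eligible class, with cross-references;
- state in Section 12 how a patient started below 840 mg counts in the six-patient DLT assessment and among the 24 at the MTD;
- make clear that class A impairment is not the same as a normal 5-point score in Appendix 4, and how the two are told apart;
- correct the Appendix D reference to Appendix 4.

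Which exclusion and which dose are right is for the sponsor to settle. The cost is an amendment to wording. It calls for no extra patients and no new analysis.
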